Efter opringning til Akuttelefonen 1813 vil forældre til børn i alderen 6 mdr. til 11,9 år blive tilbuddt at deltage. De vil blive informeret om, at de ved deltagelse får tilsendt et link til materialet på deres smartphone, og at de kan se materialet i 72 timer. De vil også få at vide, at ved deltagelse får de næste dag tilsendt et link til et SMS-spørgeskema med 6 korte spørgsmål, samt at deres barns journal igennem de næste 72 timer bliver læst, hvis barnet kommer på hospital. Der vil blive trukket lod om deltagelse. Forældrene der får materialet skal ringe 1813 igen, hvis de ønsker at tale med en sygeplejerske eller læge. Hvis de ikke får tildelt materialet kommer de til at tale med en sygeplejerske eller læge som vanligt.

Forskingsspørgsmålene vil blive besvaret udfri forældres svar på SMS-spørgeskemaet.

Første forskningsspørgsmål: Angav flere forældre, der fik adgang til materialet, høj grad af self-efficacy og empowerment end forældre, der ikke fik adgang til materialet?

Andet forskningsspørgsmål: a) Oplyste forældre, der fik adgang til materialet, i mindre grad, at deres børn var blevet undersøgt af læge end forældre, der ikke fik adgang til materialet, b) Angav forældre, der fik adgang til materialet, hyppigere høj grad af tilfredshed med kontakten til 1813 end forældre, der ikke fik adgang til materialet?

Samtlige projektdata vil blive fuldt anonymiserede, så det ikke på nogen måde er muligt at henføre data til personer. **Sikkerhed ved projektet** bliver undersøgt ved gennemgang af hospitalsjournaler af alle de inkluderede børn indenfor de næste 72 timer efter opkaldet. Ved utilsigtede hændelser vil en sikkerhedskomité tage stilling til om projektet skal afbrydes.

Det forventes, at forskningsspørgsmålene kan besvares indenfor en dataopsamlingsperiode på 3 mdr. Projektet vil ikke forløbe i længere tid end 6 mdr.

Appendix 1 viser hvorledes forældrene vil blive informeret om projektet og hvordan der vil blive indhentet informeret samtykke, samt de 6 SMS-spørgsmål der udsendes dagen efter opkaldet.

Introduction

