A prospective randomized controlled trial taking place in the Capital Region of Copenhagen including parents who call the medical helpline 1813 about a sick child aged from 6 months to 11.9 years. Excluded are parents who are not able to speak Danish, who have no Danish telephone number or have no smartphone, children with an injury and those who have participated in the study within the last 72 hours.

The parents who call 1813 will be offered to participate in the study. If they accept, they will be randomized 1:1 to the intervention group (randomized to the new material composed of 8 videos and corresponding smart cards) or to the control group (randomized to current standard care). If the family is randomized to the new material it will be possible to use this material within the next 72 hours after the initial contact to 1813.

The next day in the month at 12 a.m. (at least 12 hours after the call) the participants in the study will receive a text-message with 6 questions, for these questions see Appendix 1. If the parents do not answer the text-message they will get the text-message the following day at 12 a.m.

All case reports of the included children at the hospitals will be reviewed within 3 to 8 days after the call to register the number of children who went to departments of Paediatrics, the diagnosis, if the children had examinations or treatment, if the children were sent home from the hospital or admitted to the departments of Paediatrics, the duration of hospitalization, intensive care admittance and mortality within 72 hours after the initial call.

At the Copenhagen Emergency Services the included patients in the study will be identified, and it will be noted the number and the time of further contacts to the medical helpline within the next 72 hours, and if the child was referred to hospital.

Moreover, for every included parent and child (family) it will be noted the number and time the family used the new material, and which kind of the material was used and for how long time.

To investigate if bias was present in the study we want to study: age, sex, if the patients were referred to hospital, admitted to hospital, the duration of hospitalization, intensive care admittance and mortality within 72 hours after the initial call. We also want to study: age, sex, if the patients were referred to hospital for the patients who accepted to participate in the study versus those who did not accept to participate.

Aim of the study

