Did the new material about sick children result in high parental self-efficacy among the parents who were allowed to watch the material?

Did new material about sick children result in less children examined by a doctor and more satisfied parents?

Primary outcome

Data of the electronic questionnaire from the parents;

High parental self-efficacy defined as parents who answered "i meget høj grad" or "i høj grad" to at least two of the three questions:

"Hvor godt kunne du passe dit syge barn hjemme, efter du søgte hjælp ved at ringe 1813?",
"Ved du hvad du kan gøre hjemme, hvis dit barn får samme symptomer en anden gang? and
"Ved du, hvornår det er så alvorligt, at du skal kontakte læge eller 1813, hvis dit barn får samme
symptomer en anden gang?"

Secondary outcomes

Data of the electronic questionnaire from the parents;

- Use of professional consultations: Yes to the question "Har en læge/sygeplejerske undersøgt dit barn under dette sygdomsforløb?" (både egen læge og læge på hospital).
- Satisfied with the contact to the acute telephone 1813: Yes (svar "i meget høj grad" og "i høj grad") to the question "Er du overordnet tilfreds med den hjælp du fik, da du kontaktede 1813?"

Exploratory outcomes

Data of the electronic questionnaire from the parents;

- The medical status of the sick child "Hvordan har dit barn det nu, sammenholdt med da du kontaktede 1813?"

Data from the Copenhagen Emergency Services;

- The number of telephone contacts to 1813, the age and the sex of the child.
- The number of parents who called 1813 within the next 72 hours after the initial call.
- The number of patients, who were referred to a hospital within the next 72 hours after the initial call.

Data of the calls from the videos and action cards;

- The number of times the 8 videos and the eight action cards were used within the next 72 hours after initial contact to 1813.
- The duration and types of videos and action cards the parents watched within the next 72 hours.

Data from the case reports from Epic (Sundhedsplatformen);

- The number of patients, who went to a hospital within the next 72 hours after the initial contact to 1813, and the time of arrival.
- The number and diagnoses of patients who did neither get treatment nor paraclinical tests, but merely parental medical at hospital.
- The number and diagnoses of patients who went home from the hospital with treatment for example antibiotics or painkillers.

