- The number of number and diagnoses of sick children who were inpatients in less than 12 hours, more than 12 hours, more than 24 hours in the following 72 hours or went to the intensive care unit.

Automatic speak when the parents call 1813 and the SMS-questions the next day

Please notice **Appendix 1**, in Danish, for specific information.

Safety measures: The paediatric departments in the Capital Region will be made aware of the study. The case reports of the included children at the hospitals will be reviewed within 3 to 8 days after the call. This will primarily be done by the ph.d. student doctor, who is blinded for the information of the study group (intervention versus control group). We will register the number of children who went to departments of Paediatrics, the diagnosis, the duration of hospitalization, intensive care admittance and mortality within 72 hours after the call. It will also be noted, if there are cases of unexpected serious adverse events, near-misses, death, and if it looked as if the child went to hospital later than optimal based on parental delay. In these cases, this information will be presented for a **Data Safety Committee** and it will be revealed if the child was randomized to the intervention or to the control group. The **Data Safety Committee** will advise the study group on continuation, modification, or stopping the trial.

Sample size

We want to be able to detect if the intervention with videos and action cards increases the proportions of parents who expressed high self-efficacy by 5%. We do not know this actual proportion. If it is actual 50%, we want to detect an increase to 55%. We want a p-value of 0.05 and a probability (power) of 80%.

It will require data from about 3300 text-messages (SMSs) in total, randomized in two equal groups (<http://www.openepi.com/SampleSize/SSCohort.htm>).

If the baseline is at a higher level, for example 70% then we want an to be able to detect an increase to 75%, and with the same p-value and power we then require totally 2520 SMSs.

There are about 160.000 calls concern children of at least 6 months of age to the medical helpline 1813 (18).

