The parents are informed about the study by an automatic voice in the phone and if they press 1, the value for accept, it is taken as their informed consent. The project will be described in short, like this protocol resumé in Danish, at the webpage of the Copenhagen Emergency Service, and it will be possible to link to the study at <https://clinicaltrials.gov/>.

The telephone call will be recorded in the Emergency Medical Services system, based on the actual regular routine. Before initiating the study, the protocol will be submitted to the ethics committee of the Capital Region in Denmark, which may consider it outside their mandate. In this case the project will be submitted to "Videncenter for dataanmeldelse, Rigshospitalet".

In the project the data will be completely anonymized and it is in no way possible to link data with actual people.

The study will be registered at <https://clinicaltrials.gov/> before enrolment of the first patient.

After the first 400 SMS-answers, we will perform an interim analysis to study the frequency of acceptance, and the frequency of high self-efficacy, as well as how the videos have worked technically. Moreover, we will study if the number of SMS-answers from the two groups of families, those randomized to intervention and those randomized to control, are about the same size.

After the first 1000 SMS-answers, we will also make an interim analysis to study the effect of the videos and the action cards. This will also include an examination of a significant difference is exhibited between the number of children staying at home the day the parents call 1813 after having the possibility to watch the videos and read the action cards.

Collaborators

The project will be done in cooperation between the project group of "Børnelægernes Børnetips", the Copenhagen Emergency Medical Services, the Headquarter at the Capital Region of Denmark and the Faculty of Health and Medical Sciences, University of Copenhagen, Denmark.

The group “Børnelægernes Børnetips” consists of about 15 doctors who are paediatricians or coming-up paediatricians who cooperate with “Children’s Life - see my heart! (Børneliv – se mit hjerte!). A non-profit medical organization run by young doctors www.boerneliv.org, which has experience in doing videos of sick children and in teach children and their teachers in how the body works and emergency help.

Project applicants

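### The late-arrival safety flag covers only parental delay, so delay from the intervention arm's call-again step can go unflagged, and no by-arm timing report to the Data Safety Committee is planned

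*Combined protocol and SAP*

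**What the plan says.** The Safety measures section has hospital case reports reviewed 3 to 8 days after the call, primarily by a doctor blinded to arm. The reviewer notes deaths, near-misses and unexpected serious adverse events, and also "if it looked as if the child went to hospital later than optimal based on parental delay". Such cases go to the Data Safety Committee, and at that point "it will be revealed if the child was randomized to the intervention or to the control group". The section defines neither lateness nor a time measure, and has no category for delay arising from the helpline or from the trial.

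The Danish protocol summary describes different access in the two arms. For the intervention arm: "Forældrene der får materialet skal ringe 1813 igen, hvis de ønsker at tale med en sygeplejerske eller læge". For the control arm: "Hvis de ikke får tildelt materialet kommer de til at tale med en sygeplejerske eller læge som vanligt".

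Timing data are planned elsewhere. Exploratory outcomes include the number of patients "who went to a hospital within the next 72 hours after the initial contact to 1813, and the time of arrival". Set up records "the number and the time of further contacts to the medical helpline within the next 72 hours". Ethics and transparency adds, for the initial contact: "The telephone call will be recorded in the Emergency Medical Services system". Arrival time is not among the items registered under Safety measures, and the Statistics section leaves the method for all exploratory outcomes open.

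**The concern.** The foreseeable harm of replacing a first conversation with a link is that a child who needs hospital gets there later. In this design one source of such delay comes from allocation itself, because only intervention parents must make a second call to speak to staff. A family that uses the link, rings again and then goes to hospital has done what the trial asked. A reader who takes the criterion at its word need not call that parental delay, and the case then stays off the committee's list.

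At stake is how a reassuring result would be read. A finding of no excess of late arrivals in the intervention arm could partly reflect a definition that leaves out the delay specific to that arm. It matters more here because fewer children examined by a doctor is itself an aim: appropriate home care and late care both lower early attendance, and a list of individually flagged cases cannot show a general shift in timing.

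**Working it through.** **1. The passages side by side.**

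| Item | Intervention | Control |
|---|---|---|
| Reaching a nurse or doctor (Danish summary) | second call needed | first call |
| Late-arrival flag (Safety measures) | parental delay only | parental delay only |
| Death, near-miss, unexpected serious adverse event (Safety measures) | to committee, any cause | to committee, any cause |
| Time of hospital arrival (Exploratory outcomes) | collected for attenders | collected for attenders |
| Time of repeat 1813 contacts (Set up) | collected | collected |
| By-arm timing report to committee | none stated | none stated |

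The flag is worded the same for both arms, but only one arm has a trial-created step that the wording can leave out. What remains uncovered is late arrival without a reportable event, and any systematic shift in timing between arms.

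**2. Whether another provision covers this.** The section on stopping early names serious adverse events and very low satisfaction. The look after 400 answers covers acceptance, self-efficacy, technical function and balance of responses. The look after 1000 answers covers effect, including the number of children staying at home on the day of the call. That last item is the nearest to a timing comparison, but it is not addressed to the committee and does not follow arrivals over 72 hours.

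**3. Potential exposure.** The plan's intake figures reproduce: 160,000 × 0.25 / 365 = 109.6, about 110 families a day; 110 × 0.40 = 44 answers a day; 2520 / 44 = 57 days and 3300 / 44 = 75 days. From these:

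- Families: 110 × 57 = 6270 to 110 × 75 = 8250.
- Per arm at 1:1: 3135 to 4125.
- At the 2018 share referred to hospital (40%): 3135 × 0.40 = 1254 to 4125 × 0.40 = 1650.
- At the 2018 share sent directly to a paediatric department (10%): about 314 to 413.

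The shares come from all 2018 calls about sick children. Applying them to consenting families with children of at least 6 months is an assumption.

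**4. Whether a by-arm report would be informative.** For a cumulative incidence p with n randomised per arm, the 95% half-width for the difference is 1.96 × √(2p(1 − p)/n).

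- p = 0.40: 1.96 × √(0.48/3135) = 0.024; 1.96 × √(0.48/4125) = 0.021.
- p = 0.10: 1.96 × √(0.18/3135) = 0.015; 1.96 × √(0.18/4125) = 0.013.

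At full intake, the difference in arrivals by a given time would be estimated to within about 1.3 to 2.4 percentage points.

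Among attenders only, with m = 314 to 1650 per arm, the difference in call-to-arrival time detectable with 80% power is (1.96 + 0.84) × √(2/m) = 0.22 down to 0.10 SD. Numbers are not the obstacle there. The obstacle is that attenders are selected after randomisation, by a process the intervention may change.

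**The case against.** The strongest reply is that the committee already sees the cases that matter most. Deaths, near-misses and unexpected serious adverse events reach it without any limit on cause, so a child harmed or nearly harmed after watching and calling again is covered. Diagnosis, length of stay, intensive care and mortality are also registered for children who reach hospital. This stands, and it narrows the gap to late arrival without such an event and to shifts in timing. The registered items do not close that gap, because no by-arm report of them to the committee is stated.

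Second, the parents decide when to ring again, so a reader could reasonably code that interval as parental delay. A blinded reader, who may not know a second call was required, might be more inclined to do so. This also stands: under-counting in one arm is possible, not shown. Appendix 1, with the wording given to parents, was not fully available for this review and might bear on it.

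Third, call-to-arrival time exists only for children who go to hospital, and must be derived by linking helpline and hospital records. A longer average among intervention attenders could reflect a different mix of children. This stands, and it determines the denominator in the fix.

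A reader might also infer that revealing the arm with a flagged case biases the assessment of delay. The documents do not support this. Lateness is judged primarily by a blinded doctor before the arm is revealed, and the committee's stated task is to advise on continuing, modifying or stopping the trial, not to classify delay. Showing the arm to a body with that task is not a defect.

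**Conclusion.** The point holds in limited form. The late-arrival flag is an impression tied to one cause, and only one arm has a trial-created step outside that cause. Late arrival due to that step can go unflagged unless it ends in an event reported on other grounds. The timing data that would show it are planned, but not for the committee.

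The size of any under-count cannot be derived from the documents. The 1250 to 1650 intervention children, of whom about 310 to 410 are of the direct-referral type, measure potential exposure. They rest on the plan's intake assumptions, on 2018 referral shares applied to consenting families, and on those families ringing again, although a second call is required only if they want to speak to staff. A reader might take them as children delayed or missed; nothing in the documents supports that. A reader might also conclude that trial-created delay will be missed, or that safety monitoring ignores it. The cause-free reporting of serious events rules out both statements as worded.

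The change is worth making before enrolment, because it costs little and bears on the harm most specific to this design.

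**What to change.** In Safety measures:

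- Have the blinded reviewer flag late arrival from any cause, counted from the initial randomised call, and record the apparent cause in a separate field. What counts as late is for the investigators to define.
- Give the Data Safety Committee, by arm, the cumulative incidence of hospital arrival over 72 hours from the initial call among all randomised children, together with admissions and intensive care admissions per randomised child and time to a repeat 1813 call.
- Show call-to-arrival time among attenders as descriptive only, because the intervention may change who attends.

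The cost is a few more cases to present and one extra table. The table uses data already planned, but helpline and hospital records must be linked by child before anonymisation, under the permits that the Statistics section mentions. Revealing the arm for individual flagged cases already presupposes a link between record and allocation. No treatment, referral or call-handling rule changes.

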If we suggest that 25% of the parents to the sick children agree to be randomized, and that 40% of the included parents answers the text-message the next day, then we can include $(160,000 \times 0.25)/365 =$ about 110 children a day, and we will get about 44 text-messages a day. Then we need $2520/44 - 3300/44 = 57- 75$ days to include enough patients. It is less than 3 months.

In the data from the Copenhagen Emergency Services, and data from the safety measures we will not have loss to follow up, since data from the Copenhagen Emergency Medical Services and from all four Departments of Paediatrics in the Capital Region are collected routinely.

In the data of the calls from the cases we also suggest that all contacts are safety stored so we will have no loss to follow-up.

We suggest we have data to answer our research question within 3 months, and the study will be stopped after 6 months.

Stop of the study before an answer our research question

In cases of serious adverse events the study group will consider stopping the study. This will also be the case if the satisfaction with the contact to the acute telephone 1813 drops to a very low level.

Statistics

The primary analysis will use Chi-square and a two-sided level of significance of $p < 0.05$ for the primary outcome and a $p < 0.025$ for the two secondary outcomes. All other outcomes are exploratory and the statistical methods will be adapted as appropriate. The results from these exploratory analyses will not be used to claim clinical efficacy but used to design new studies. This is an important aspect since new studies can be rapidly designed and performed once the project set-up is in place.

The dataset will be rich and allow exploration of the effect of individual videos, as well as subgroup analyses.

We believe that our set up is robust, as the sick children are included based on electronic equipment, not adding extra work on the medical personnel, the operators. The follow up to the parents by text message the next day is also based on electronic equipment and the follow-up in the medical case reports after 72 hours, for safety reasons, is based on easily available information, if we have the relevant permits for this.

Ethics and transparency

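### The primary outcome is tested only in parents who answer the SMS, and no sensitivity analysis covers the families who do not answer

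*Combined protocol and SAP*

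**What the plan says.** - **Outcome.** The Primary outcome section takes the endpoint from the SMS questionnaire alone: "High parental self-efficacy defined as parents who answered" in the top two categories on at least two of three questions.
- **Sample size.** It is counted in answers: "It will require data from about 3300 text-messages (SMSs) in total" for 50% versus 55%, and 2520 for 70% versus 75%. The same section assumes that "40% of the included parents answers the text-message the next day".
- **Analysis.** Under Statistics: "The primary analysis will use Chi-square and a two-sided level of significance". No analysis set, missing-data method or sensitivity analysis is named.
- **Reminder.** Under Set up: "If the parents do not answer the text-message they will get the text-message the following day". No final reply rate is given.
- **Bias checks.** Set up also says: "To investigate if bias was present in the study we want to study: age, sex, if the patients were referred to hospital", followed by admission, length of stay, intensive care and mortality. That sentence does not say which groups are compared. The next sentence compares parents who accepted with parents who declined, on age, sex and referral.
- **Interim check.** Under Ethics and transparency: "After the first 400 SMS-answers, we will perform an interim analysis to study the frequency of acceptance". At that point "we will study if the number of SMS-answers from the two groups of families" are similar.
- **Routine data.** Set up and Sample size say that helpline and hospital data will be collected for all included children, with none expected to be lost.

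**The concern.** No analysis set is named. But the outcome exists only for parents who answer, so a chi-square test without imputation uses only them. On the planning figure, most randomised families contribute nothing to the primary comparison, and the plan does not say how the conclusion would be tested against that.

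The replier difference is biased in either of two situations:
- the gap between repliers and non-repliers differs between arms;
- the gap is the same in both arms, but the reply rates differ.

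Both are plausible, because the arms have different experiences before the questionnaire arrives. According to the Danish summary, intervention parents must ring 1813 again to reach a nurse or doctor, while control parents speak to one as usual. Selective reply could create an apparent benefit or hide a real one.

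A separate, minor point concerns referral. The comparison of acceptors with decliners pools both arms. Half of the acceptors receive the material and must ring again before 1813 staff can refer the child, so a difference from decliners mixes selection with a treatment effect. Age and sex are not affected.

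**Working it through.** **1. The plan's own figures.** Two-sided 5% level, 80% power, 1:1 allocation. For 50% versus 55% the total is 3130 without and 3210 with continuity correction (plan: about 3300). For 70% versus 75% it is 2502 and 2582 (plan: 2520). Inclusion is 160,000 × 0.25 / 365 = 109.6 a day, and × 0.40 gives 43.8 answers. Then 2520/44 = 57 days and 3300/44 = 75 days, as stated. The sample size is not in error. The 40% allows for the number of answers, not for who answers.

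**2. Families without the outcome.** At 40% reply, 3300/0.40 = 8250 randomised, so 4950 are missing; 2520/0.40 = 6300, so 3780 are missing. The 40% is a next-day figure, before the repeat SMS. For 3300 answers, an assumed final rate of 50% leaves 6600 − 3300 = 3300 missing, and 60% leaves 5500 − 3300 = 2200.

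**3. Formula.** Let r be an arm's reply rate, and d the non-replier rate minus the replier rate in that arm, in points (I intervention, C control). Then

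all-randomised difference = replier difference + (1 − rI)·dI − (1 − rC)·dC.

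For fixed shifts the standard error is that of the repliers.

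**4. Equal reply, different gaps.** Assume 55% versus 50% is observed with 1650 repliers per arm. SE = √(0.55×0.45/1650 + 0.50×0.50/1650) = 1.74 points. The lower 95% limit is 5 − 1.96×1.736 = 1.6 points. At 40% reply the difference is 5 + 0.6·(dI − dC):

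| dI | dC | Difference | z |
|---|---|---|---|
| −10 | −10 | 5.0 | 2.9 |
| −5 | 0 | 2.0 | 1.2 |
| 0 | +5 | 2.0 | 1.2 |
| −5 | −10 | 8.0 | 4.6 |

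- Significance is lost at dI − dC = −1.60/0.60 = −2.7. The effect is zero at −5/0.60 = −8.3.
- At an assumed 50% reply these become −3.2 and −10.0; at 60%, −4.0 and −12.5.
- For 75% versus 70% with 1260 per arm at 40% reply, SE = 1.78 and significance is lost at −2.5.
- In the other direction, an observed 52.5% versus 50% (SE 1.74, p = 0.15) becomes significant at (1.96×1.740 − 2.5)/0.60 = +1.5.

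**5. Equal gap, unequal reply.** Assume dI = dC = −20 with 35% reply (intervention) and 45% (control). Then 5 + 0.65×(−20) − 0.55×(−20) = 5 − 13 + 11 = 3.0 points, and z = 3.0/1.74 = 1.7. Significance is lost although the gap is the same in both arms.

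**6. What the interim count check can see.** At 40% reply, 400 answers come from 1000 families, 500 per arm. The SE of the difference in reply rate is √(2×0.24/500) = 3.1 points, so the 95% half-width is 6.1 points. With 4125 per arm at the end it is 2.1.

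Equal counts also do not exclude outcome-related reply. Assume no true effect, 50% high self-efficacy in both arms, and control parents replying at 40% whatever their outcome. If intervention parents reply at 44% when self-efficacy is high and 36% when it is low, their overall rate is 0.5×0.44 + 0.5×0.36 = 40%, so the counts match. Yet repliers show 0.22/0.40 = 55% versus 50%, and the test is significant about 82% of the time.

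**7. Referral comparison.** With half the acceptors treated, the spurious difference is half of any treatment effect on referral. Assume 40% referral (the Introduction's 2018 figure), 8250 acceptors and, at 25% acceptance, 33,000 − 8250 = 24,750 decliners. SE = √(0.24/8250 + 0.24/24,750) = 0.62 points. With control-arm acceptors only it is √(0.24/4125 + 0.24/24,750) = 0.82.

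**The case against.** Several counter-arguments have force.

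- **The plan is not silent on response bias.** It has a repeat SMS, a list of variables for examining bias and a check of answer counts by arm. This stands and deserves credit. But the acceptor/decliner comparison concerns consent, not silence after randomisation; the count check is imprecise and blind to outcome-related reply; and no replier versus non-replier comparison is stated.
- **The 2.7-point threshold looks alarming partly by construction.** It describes a result exactly at the target effect, where the lower limit is only 1.6 points before any shift. This stands: a larger observed effect would be more robust.
- **40% may not be the final rate.** This also stands, so 4950 should not be read as the expected number missing without the 50% and 60% figures beside it.
- **Selective reply need not cause bias.** A common gap with equal reply rates leaves the difference unchanged (first row of the table). But a common gap is not harmless in general, as step 5 shows.
- **The gap could be examined anyway.** A reader might infer that the trial would be unable to do so. The documents do not support that. A tipping-point table needs only counts by arm, and the routine data appear to make imputation feasible. What is missing is the specification.
- **The referral comparison is descriptive.** No test or claim is attached to it, so it is a minor correction.

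**Conclusion.** The concern holds as a gap in the planned analysis. The primary test is in effect complete-case, with 60% of outcomes missing at the planning rate (50% or 40% missing at the assumed higher rates), and no analysis is specified to show whether the conclusion depends on those families. At an observed 55% versus 50% and equal reply, a between-arm difference in the non-replier shift of 2.7 to 4.0 points against the intervention removes significance across reply rates of 40% to 60%. These thresholds treat the shifts as known and the observed result as exactly on target.

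A reader might go further and infer that the trial's result is biased. The documents do not support that: they show different call paths by arm, which makes differential reply plausible, but give no evidence that it occurs or in which direction. The replier test remains usable as primary and the sample size needs no change, but the supporting analyses should be fixed in advance. The referral point holds as a minor correction.

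**What to change.** 1. Keep the chi-square test in repliers as the primary analysis, and name that population.
2. Pre-specify one sensitivity analysis of all randomised families: multiple imputation done separately by arm, using age, sex, renewed contact with 1813, 72-hour referral and hospital attendance and, in the intervention arm, recorded use of the material.
3. Imputation corrects selective reply only as far as these variables predict self-efficacy. So add a two-way tipping-point table that uses each arm's observed reply rate and shifts non-repliers in each arm independently, in both directions, far enough to show where significance and the sign change.
4. At the end of the trial, report the reply proportion by arm, and compare repliers with non-repliers within each arm on the variables in the Set up bias list.
5. Minor: compare decliners on referral with control-arm acceptors only; keep all acceptors for age and sex.

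**Cost.** No extra families. A coded link between answers and routine records must be kept until analysis, with anonymisation afterwards. Some link during the trial is already implied by the record review and the revealing of the arm under Safety measures, but the anonymisation statements and the record-access permits mentioned under Statistics must be settled accordingly. Imputed intervals may be slightly wider. The referral check loses some precision (SE 0.62 to 0.82 points under the assumptions in step 7).
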